Cover paper

Research title: (The effect of two and four activations daily of the periodontal distractor on pain intensity and pulp vitality of maxillary canine: Randomized Clinical Trial)

Study Start: February 1, 2021 [Actual]

Primary Completion: August 1, 2022 [Actual]

Study Completion: October 15, 2022 [Actual]

Objectives:

Since the periodontal distractor may cause some degree of suffering for the patients and may affect pulp vitality, Therefore the aim of the present study was to evaluate the effect of twice and four activations day of periodontal distractor on pain intensity and pulp vitality of maxillary canine.

Methodology:

PICO:

- Problem: orthodontic patients that have
 - (1)Class I malocclusion severe crowding or bi maxillary protrusion
 - (2)Class II div 1 malocclusion.
- Intervention: performing bilateral maxillary 1st premolar extraction, inter septal bone cuts then placing periodontal distractor and activate it till complete canine retraction.
- Comparison: two versus four activation per day.
- Outcomes:
 - Pain intensity.
 - Pulp vitality.

Study design

The study was randomized control study. It was conducted in a sample of 32 canines on 16 female patients attending the Faculty of Dental Medicine for Girls, Al Azhar University, seeking for orthodontic treatment. Their age was ranged from 16 to 22 years. This prospective study was approved by Research Ethic Committee (REC), Faculty of Dental Medicine for Girls, Al Azhar University with this code (REC-OR-21-01) Fig. (8) Showing CONSORT 2010 flow diagram of this study.

All study participants have signed on written informed consent prior to enrollment. The steps of the study, the aim, the potential benefits, and hazards, all were discussed with the patients.

Sample size calculation:

To Compare the effects of two different orthodontic treatment modalities on pain; independent t test was used for comparison between groups. According to a previous study by Raza et al (2021), Mean VAS scores were 16 ± 3.94 (24 hours) at control side, in comparison to 46.50 ± 6.69 (24 hours) A minimum total sample size of 6 samples on each group are sufficient to detect the effect, by increasing 2 patients on each group to overcome dropping out of patients, the number were 8 on each group and 16 on both groups (fig 1).

Patient Records

Inclusion criteria were: 1-Orthodontic Patients need extraction of first permanent premolar for orthodontic reasons (dentoalveolar maxillary protrusion, Class II div 1 malocclusion), 2-No history of previous orthodontic treatment, 3- Absence of any systemic disease, 4- Good oral hygiene and healthy gums look, with no signs of redness, edema, or bleeding during brushing (periodontal inflammation), 5- Highly motivation and cooperation

Exclusion criteria were: 1- Medically compromised patients, -2-Use of medication that may affect tooth movement during the period of the study.

After patient selection, routine records of all the patients such as a detailed case history, pretreatment study model, extraoral and intraoral photographs, panorama and lateral cephalometric radiographs were acquired. Pain intensity and discomfort was evaluated at different times by Visual Analogue scale (1st 48 hour after intervention, during each activation of the distractor, and on the Interval between activation) as research related records. Electric pulp testing of canine was done before and after retraction to evaluate pulp vitality.

All the patients in the study required bilateral first premolar extraction. They were divided into two groups (Group I): Canine retraction was done by periodontal distractor with twice activations per day. (Group II): Canine retraction was done by periodontal distractor with four activations per day.

Randomization Allocation concealment:

Randomization was accomplished using online research randomizer. Numbers were from 1 to 16 and each group contained 8 numbers. Set 1 of numbers was assigned to periodontal distractor with two activations per day. Set 2 of numbers was assigned to periodontal distractor with four activations per day. The randomized numbers for the participant were written in opaque white papers which were folded, codes for randomization were kept with another investigator. Allocation of each patient to either group was done by picking up by a colleague with allocation ratio 1:1.

Study phases: This study included four phases:

Phase I: Posterior segment leveling and alignment:

For patients of both groups the orthodontic treatment was started with direct bonding of Roth brackets (Dynaflex,USA) to the maxillary canine, second premolars first molar only. Sectional nickel titanium (NiTi) arch wires were used starting from

0.014" up to stainless steel arch wire 0.016"×0.022". This was undertaken to align the posterior segment before premolar extraction to allow proper placement of distractor without canting. Fig. (1).

Figure (1) After leveling and alignment of posterior segment with sectional wire.

Phase II : Extraction and inter septal bone corticotomy phase.

Patients were referred to the clinic of Oral and Maxillofacial Department, Faculty of Dental Medicine for Girls, Al Azhar University to extract first maxillary premolars with written referral note. The post extraction instructions were firm and clear not to use NSAIDs drugs for analgesia, paracetamol drugs were prescribed¹.

The second step consisted of performing corticotomies (grooves) in the interseptal bone distal to the canine with bur. Initially, two vertical grooves were done inside the extraction socket, along the buccal and lingual sides then, another groove that was extended obliquely toward the base of the interseptal bone to weaken its resistance Fig. (2). The depth of the undermining grooves was dependent on the thickness of the interseptal bone, as revealed on the Periapical films that was done immediately after extraction . Corticotomy was done by surgical bur on straight hand piece (Apple dental, china) using normal saline for irrigation to prevent adverse thermal changes in the periodontium.

Fig. (2) Inter septal bone Coricotomy with surgical bur on straight hand piece

Phase III: Periodontal distractor construction and placement:

A Hyrax screw(Dentauram, Germany) was modified to form a distractor. Bands on molar and canine were placed with a lingual button welded for the attachment of the elastomeric chain, to counteract any rotation force that was encountered by the canine during the distraction process.

The screw was opened slightly more than the width of premolar to be extracted and extended arms were bent to desirable shape to be soldered on molar and canine bands. The distractor was placed and cemented by glass ionomer cement Fig. (3).

[figure not shown]

Fig. (3) Steps of periodontal distractor appliance construction from hyrax screw.

Phase IV: Activation of periodontal Distraction Fig. (4) :

Group I : The canine was distracted two per day for a total about 0.4 mm per day.

Group II: four activations of 0.2 mm each for a total about 0.8 mm per day.

The distractor was activated till the distal surface of canine became in contact with the mesial surface of second premolar Fig. (5).

The patients were instructed to apply orthodontic wax on the superior edges of distractor immediately after its placement to minimize discomfort of the oral mucosa as a result of trauma and friction between mucosal tissue and the distractor.

Fig. (4) Activation of periodontal distractor with key

Fig. (5) Before and after complete canine retraction by periodontal distractor

Measurement of pain: Pain intensity and discomfort was evaluated at different times by Visual Analogue scale (1st 48 hour after intervention, during each activation of the distractor, and on the Interval between activation) Fig. (6) .

[figure not shown]

Fig. (6)Visual Analogue scale of pain.

Measurements of Pulp vitality:

The distracted canine's pulp was recorded with noninvasive, simple and clinically popular device. It was electric pulp tester.

The tip of the probe of EPT (Denjoy, china) was applied on sound enamel on the midpoint of each tooth. This area is the most effective site for EPT because of its close proximity to the highly innervated area of canine crown and because it provides a readily reproducible position. An interface medium as tooth paste was placed on tooth after its dryness with air spray to conduct electrical impulses to the tooth. The device has a numeric scale, and these numbers have been used to register changes in test responses Fig. (7).

[figure not shown]

Fig.7 : Measurement of pulp vitality with electric pulp tester.

[figure not shown]

Fig. (8) CONSORT 2010 flow diagram of patients' recruitment and follow-up

Statistical analysis:

Comparison between different intervals was performed by using Friedman's test (non-parametric data). Comparison between both groups was performed by using Mann Whitney's test (non-parametric).

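### The unit of analysis for pulp vitality is not stated: 16 patients are randomised but the sample is given as 32 canines, and a 16 vs 16 canine Mann-Whitney would exceed its nominal 5% error

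*Combined protocol and SAP*

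**What the plan says.** - **Study design** counts both teeth and patients: "It was conducted in a sample of 32 canines on 16 female patients".
- **Sample size calculation** counts patients in its final step: "the number were 8 on each group and 16 on both groups".
- **Randomization Allocation concealment** also counts patients: "Numbers were from 1 to 16 and each group contained 8 numbers", and "Allocation of each patient to either group was done by picking up by a colleague".
- **Patient Records** makes treatment bilateral, "All the patients in the study required bilateral first premolar extraction", and sets the pulp measurement: "Electric pulp testing of canine was done before and after retraction to evaluate pulp vitality".
- **Measurements of Pulp vitality** takes the reading on the tooth; the probe "was applied on sound enamel on the midpoint of each tooth".
- **Statistical analysis** is two sentences. One names Friedman's test for changes over time. The other covers the groups: "Comparison between both groups was performed by using Mann Whitney". It names no unit of analysis, no way of combining a patient's two canines, no allowance for clustering and no significance level.

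**The concern.** This is not a split-mouth design. Each patient goes to one regimen and contributes two canines to it. The Mann-Whitney test assumes independent observations, and two canines in one mouth, tested on the same person, are unlikely to be independent. If the 32 canines are entered as 16 vs 16, any positive correlation within patients makes the p-value too small. A chance difference between two sets of 8 patients could then be reported as an effect of activation frequency on pulp vitality, one of the trial's two outcomes.

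Because the unit is unstated, two analysts following the same text could report different sample sizes and different p-values for the same comparison.

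Pain is a lesser issue. The documents do not say whether the VAS was scored once per patient or once per side. Pain is affected only if it was scored per side, or if one score was entered for both canines.

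**Working it through.** **Inputs from the documents.** 16 patients, 8 per arm, allocated as whole patients; 2 canines per patient; pulp test read per tooth; Mann-Whitney between groups.

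**Assumptions.** Two-sided 5% (no alpha is stated). ICC between a patient's two readings from 0 to 1 (none is given).

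**The plan's own counts.** 6 + 2 = 8 per group; 8 × 2 = 16 patients; 16 × 2 = 32 canines. These agree with each other. The figure of 6 per group does not follow from the quoted VAS values: the pooled SD is √((3.94² + 6.69²)/2) = 5.49, the standardised difference is 30.5/5.49 = 5.56, and an independent t test already has 99.8% power with 3 per group. That is a separate matter about pain and does not bear on the unit of analysis.

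**Step 1: approximation.** With 2 canines per patient the design effect is 1 + (2 − 1) × ICC = 1 + ICC. The effective number of canines is 32/(1 + ICC). The type I error of a test that ignores the pairing is about 2 × [1 − Φ(1.96/√(1 + ICC))]. At ICC 0.5, 1.96/√1.5 = 1.600, which gives 0.110.

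**Step 2: simulation with no treatment effect.** Readings were a normal patient effect plus canine error, with 8 patients per arm and 2 canines each, and Mann-Whitney was run on 16 vs 16 canines. Run A used 60,000 replicates and the tie-corrected normal approximation with continuity correction. Run B used 100,000 replicates and the exact cut-off (smaller U ≤ 75).

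| ICC | Effective canines | Approximation | Run A | Run B |
|---|---|---|---|---|
| 0 | 32 | 5.0% | 4.5% | 4.7% |
| 0.1 | 29 | 6.2% | 5.8% | 5.7% |
| 0.3 | 25 | 8.6% | 7.9% | 8.0% |
| 0.5 | 21 | 11.0% | 10.2% | 10.5% |
| 0.8 | 18 | 14.4% | 14.4% | 14.3% |
| 1 | 16 | 16.6% | 16.2% | 15.9% |

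The error reaches twice nominal at an ICC of about 0.45 (9.9% in run A).

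**Step 3: sensitivity to the scale.** Skewed readings rounded to integers gave 5.9%, 8.0%, 10.5% and 14.2% at ICC 0.1, 0.3, 0.5 and 0.8. At ICC 1, where each reading is tied with its partner, the normal approximation without continuity correction gives 18% to 19%.

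**Step 4: the patient as unit.** The exact Mann-Whitney on 8 vs 8 patient means (reject if the smaller U ≤ 13, size 0.0499) gave 4.9% to 5.1% at every ICC with continuous readings. With rounded integer readings it was slightly conservative, at 4.4% to 4.8%.

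**The case against.** The strongest reply is that no canine-level analysis is shown. Every group size in the plan is in patients, nowhere are 16 canines per group mentioned, and 32 canines in 16 patients is an accurate description of a bilateral procedure. On that reading the natural analysis is 8 vs 8, and the error rates above describe something that may never have been done. This stands as far as it goes: the defect is the unstated unit, and the inflation is conditional. It does not remove the point, because a test applied to tooth-level readings in a sample described in teeth can just as well be run on 32 values, and nothing in the plan prevents it.

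Other points also have some force:

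- The CONSORT diagram (Fig. 8) is not reproduced in the text examined. It may show what was counted as analysed, so a reader who has it should check.
- The size of the problem is open. At ICC 0.1 the inflation is small, and an ICC of 1 requires identical readings in both canines of every patient. The ICC of before-to-after changes may also differ from that of raw readings.
- The trial was sized on pain, which may not be affected.
- Averaging two readings treats the tester's scale as interval, can mask a single affected tooth, and needs a rule for a missing or non-responding canine. This is a fair comment on the detail of the remedy, not on the choice of the patient as unit.

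**Conclusion.** The concern holds as a conditional one. The plan randomises patients, measures teeth, describes its sample in both, and applies a test for independent observations without saying which it uses. If the pulp-test comparison is run on 16 vs 16 canines, a nominal two-sided 5% test has a true error of about 6% at ICC 0.1, about 8% to 9% at 0.3, 10% to 11% at 0.5, about 14% at 0.8 and 16% to 17% at 1. If it is run on 8 vs 8 patients, there is no inflation.

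Confidence is high in the omission and in the arithmetic. The documents do not establish that error was in fact inflated, and both the 5% level and the ICC range are assumptions. The point should be fixed because it decides whether the only between-group test of a stated outcome is valid.

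**What to change.** - State that the patient is the unit of analysis, and describe the sample as 16 patients, 8 per arm, with two canines each.
- Average each patient's two pulp-test readings, and any side-specific VAS scores, and compare arms with an exact Mann-Whitney on 8 vs 8 values. State in advance how a missing or non-responding canine enters the patient value, and list canine-level readings descriptively so that a single affected tooth stays visible.
- If canine-level inference is wanted, use a clustered rank-sum test (for example Datta-Satten) with patient as cluster. Its large-sample variance is less secure with 8 clusters per arm, so the exact patient-level test is preferable.
- Use patients as blocks in any within-group test over time.
- Say whether the VAS was scored once per patient or per side.

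**Cost.** One or two sentences of analysis text and a trivial computation. The trial is complete, but existing data are enough. The price is a smaller n and less favourable p-values. In simulation (20,000 replicates), the exact patient-mean test had power 0.83 for a difference of 1.2 canine-level SD at ICC 0.1, 0.77 and 0.83 for 1.3 and 1.4 SD at ICC 0.5, and 0.81 for 1.5 SD at ICC 0.8. So 80% power needs about 1.2, 1.35 and 1.5 SD respectively.

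### The stated minimum of 6 per group cannot be reproduced from the plan's own VAS inputs, although it is more than enough for the difference assumed

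*Combined protocol and SAP*

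**What the plan says.** The Sample size calculation section names the test used for sizing: "independent t test was used for comparison between groups". It takes its inputs from an earlier study: "Mean VAS scores were 16 ± 3.94 (24 hours) at control side, in comparison to 46.50 ± 6.69 (24 hours". From these it concludes: "A minimum total sample size of 6 samples on each group are sufficient to detect the effect". It then adds an allowance for losses: "by increasing 2 patients on each group to overcome dropping out of patients, the number were 8 on each group and 16 on both groups".

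The section on randomisation and allocation concealment uses the same numbers, 1 to 16 with eight per group, and a 1:1 ratio. The Statistical analysis section plans a different between-group test from the one used for sizing: "Comparison between both groups was performed by using Mann Whitney's test (non-parametric".

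The visible text gives no alpha, sidedness or power. The sample size paragraph refers to a figure 1, but the only Figure 1 captioned in the text shows posterior-segment alignment. A sample size figure may therefore exist that we cannot see.

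**The concern.** The sentence with the result contradicts itself, because 6 cannot be both the total and the number on each side. The inputs are also extreme. The two means differ by more than five standard deviations, and a t test needs very few patients to detect that. A minimum of 6 per group looks too large by about a factor of two.

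This calculation is the only quantitative justification for the trial's size, and 8 per group and 16 in total are built directly on the 6. A reader who takes 6 as a true minimum will think that the trial is only just able to detect 30.5 VAS points. It can in fact detect differences about a third of that size, and this affects how a null pain result would be read.

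**Working it through.** **Inputs.** From the Sample size calculation section: means 16 and 46.50, SDs 3.94 and 6.69, independent t test, 2 extra patients per group. From the randomisation section: 1:1 allocation. Assumed, because not visible: alpha 0.05, two-sided, power 80% to 99%, with other settings tried below.

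**Standardised difference.**
- Difference = 46.50 − 16 = 30.5.
- Pooled SD = √((3.94² + 6.69²)/2) = 5.49.
- d = 30.5/5.49 = 5.56. With the larger SD throughout, d = 30.5/6.69 = 4.56.

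**Attempt to reproduce 6 per group.** Power comes from the noncentral t distribution with 2n − 2 degrees of freedom and noncentrality d√(n/2). At two-sided alpha 0.05:

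| n per group | Power, d = 5.56 | Power, d = 4.56 |
|---|---|---|
| 2 | 78.9% | 65.5% |
| 3 | 99.8% | 98.2% |
| 4 | over 99.99% | 99.9% |
| 6 | over 99.99% | over 99.99% |

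With the pooled SD the minimum is 3 per group, 6 in total, at any power from 80% to 99%. The stated 6 per group is not reproduced.

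**Sensitivity to the settings that are not visible.** Minimum per group for the t test:

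| Setting | Pooled SD | Larger SD |
|---|---|---|
| One-sided 0.05, 80% power | 2 | 2 |
| One-sided 0.05, 95% power | 2 | 3 |
| Two-sided 0.05, 80% to 95% power | 3 | 3 |
| Two-sided 0.05, 99% power | 3 | 4 |
| Two-sided 0.05, 99.9% power | 4 | 4 |
| Two-sided 0.01, 99.9% power | 5 | 6 |
| Two-sided 0.001, 95% or 99% power | 5 | 6 |
| Two-sided 0.001, 99.9% power | 6 | 7 |

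At alpha 0.05 the range is 2 to 4. Six first appears at alpha 0.01 with 99.9% power, and then only with the larger SD.

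Changing the form of the t test does not help. By simulation with the unequal SDs, a Welch test has about 97% power at 3 per group. A paired t test with no correlation has 90% power at 3 pairs.

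**The planned test.** The smallest two-sided p value of an exact Mann-Whitney test with n per group is 2/C(2n, n).
- 3 v 3: 2/20 = 0.10, so p < 0.05 cannot be reached.
- 4 v 4: 2/70 = 0.029. Simulated power on the cited means and SDs is 99.9%.

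Under the planned test the cited inputs therefore need 4 per group.

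**What the enrolled numbers can detect.** This assumes 80% power, two-sided 5%, one VAS value per patient, and normal values with equal SDs.
- t test, 6 per group: 1.80 SD × 5.49 = 9.9 points, and 9.9/30.5 is about one third.
- Exact Mann-Whitney, 8 v 8 (simulation): about 1.55 SD × 5.49 = 8.5 points.
- Exact Mann-Whitney, 6 v 6 after the allowed losses (simulation): about 1.93 SD × 5.49 = 10.6 points.

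**The case against.** The strongest reply has four parts.

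First, means and SDs alone give no sample size. Without alpha, sidedness and power, one cannot say that the inputs yield exactly 3 per group, and a figure that we cannot see may have held those settings. This stands. The supportable statement is that 6 is not reproducible at conventional settings, with 3 as the answer for the most usual ones.

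Second, the plan calls 6 per group sufficient, and that is true. Only the word minimum fails. This stands too, and it sets the severity.

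Third, a reader might infer that a software output of 6 in total was carried forward as a per-group figure. The arithmetic fits, since 3 + 3 = 6, and so does the mixed wording. But the documents do not establish it. The plan goes on consistently with 6 + 2 = 8 per group, and the phrase could simply be loose English.

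Fourth, a reader might infer that the trial should have had 3 per group, or 5 with the allowance for losses. The documents do not support that, because the planned between-group test is Mann-Whitney, which cannot reach two-sided p < 0.05 at 3 v 3. On that test's minimum of 4, the same allowance gives 4 + 2 = 6 per group.

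What the reply does not do is rescue the figure. No setting tried at alpha 0.05, up to 99.9% power, gives a t-test minimum above 4.

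**Conclusion.** The sentence is wrong as written, with low severity. It gives 6 as both a total and a per-group number. As a per-group minimum, 6 compares with 2 to 4 for the stated t test at alpha 0.05 (3 for two-sided 80% to 99% power), and with 4 for the planned exact Mann-Whitney test.

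It would be wrong to conclude that the trial is undersized on its own assumption. Both 6 and 8 per group have over 99.9% power for a 30.5-point difference. What is affected is the account of what the trial was sized to detect.

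The conclusion rests on the cited means and SDs as printed and on an assumed alpha of 0.05. The detectable differences in VAS points also assume that the cited pooled SD of 5.49 applies to these patients. If it does not, only the figures in SD units carry over. Whether the cited contrast is relevant to two versus four activations is a separate question and is not judged here.

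**What to change.** Rewrite the sample size paragraph and leave enrolment unchanged.

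- State alpha, sidedness and power, and say whether 6 was a total or a per-group figure.
- Stop presenting 6 per group, and hence 8, as the output of this calculation.
- Base the statement on the planned Mann-Whitney test: at exact two-sided 5%, the cited inputs need at least 4 per group. Do not substitute 3 per group.
- Report 8 per group as the number enrolled, with its detectable difference at 80% power: about 1.55 SD for 8 v 8 and about 1.93 SD for 6 v 6. Add the 8.5 and 10.6 VAS points only with the condition that the cited pooled SD applies.

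The cost is one paragraph. The document gives actual completion dates in 2022, so this is a correction to reporting and not to conduct. The downside is that the stated justification becomes less favourable: the number enrolled no longer appears to follow from a calculation.

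### Pulp testing has a baseline reading, but the planned Mann-Whitney test takes no covariate and its variable is unnamed; rank ANCOVA on one value per patient would use the baseline at little cost

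*Combined protocol and SAP*

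**What the plan says.** The Combined protocol and SAP lists two outcomes, pain intensity and pulp vitality. On the second, Patient Records states: "Electric pulp testing of canine was done before and after retraction to evaluate pulp vitality". Measurements of Pulp vitality adds: "The device has a numeric scale, and these numbers have been used to register changes in test responses". Each canine thus has a numeric baseline and a numeric final reading from the electric pulp tester (EPT).

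The Statistical analysis section is two sentences long: Friedman's test between time points and a Mann-Whitney test between groups ("test (non-parametric data). Comparison between both groups was performed by using Mann Whitney"). It names no outcome variable, covariate or unit of analysis.

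On the unit, Study design says "It was conducted in a sample of 32 canines on 16 female patients", while Randomization Allocation concealment says "Allocation of each patient to either group was done by picking up by a colleague" and "Numbers were from 1 to 16 and each group contained 8 numbers". Sample size calculation has one stated purpose, "To Compare the effects of two different orthodontic treatment modalities on pain", and gives no EPT figure. The cover page records "Study Completion: October 15, 2022".

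**The concern.** A Mann-Whitney test on after-retraction values ignores the baseline. On change scores it uses the baseline, but with a weight fixed at 1 whatever the before-after correlation. The remark about registering changes leans towards change, but it describes the device and is not tied to the between-group test.

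Three things are at stake:

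- **Precision.** The 8 per group were justified on pain only, so precision for EPT was never planned. A real effect of activation rate on the pulp may be easier to miss than it need be.
- **Baseline imbalance.** With 8 against 8, a large chance difference in baseline EPT would distort both versions of the planned test.
- **An open choice.** While the variable is unnamed, the EPT conclusion can depend on which version is reported.

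A related gap is that the unit of analysis is unstated: patients were allocated, but the sample is counted in canines.

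**Working it through.** **1. The plan's own figure.** None exists for EPT. For pain, the difference is 46.50 − 16 = 30.5, the pooled SD is √((3.94² + 6.69²)/2) = 5.49, and the standardised effect is 30.5/5.49 = 5.56. An exact two-sided 5% t test then needs 3 per group for 80% to 99% power. The stated 6 per group is not reproduced, although it is more than enough for that effect. The plan's alpha and power are not in the text. None of this bears on EPT.

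**2. Inputs.** From the documents: two EPT readings, patient-level allocation, 8 per group. Assumed: rho from 0.2 to 0.8, equal SDs before and after, one value per patient, and an effect of 1.5 SD, which gives about 80% t-test power at 8 per group.

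**3. Variance relative to after values alone (N = 16).**

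- Change: 2(1 − rho)
- ANCOVA: (1 − rho²)(1 + 1/(N − 4)) = (1 − rho²) × 1.083

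| rho | 0 | 0.3 | 0.5 | 0.7 |
|---|---|---|---|---|
| Change | 2.00 | 1.40 | 1.00 | 0.60 |
| ANCOVA | 1.08 | 0.99 | 0.81 | 0.55 |

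If the baseline carries no information, the covariate costs about 8% in variance and one degree of freedom (critical t up 0.7%).

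**4. Simulated power (%), normal data, 1.5 SD, 40,000 trials per setting.** Quade's method ranks baseline and final values, regresses final rank on baseline rank, and compares the residuals between groups.

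| rho | 0.2 | 0.3 | 0.5 | 0.7 | 0.8 |
|---|---|---|---|---|---|
| Mann-Whitney, after | 77 | 77 | 77 | 77 | 77 |
| Mann-Whitney, change | 57 | 63 | 77 | 94 | 99 |
| Quade | 75 | 77 | 83 | 92 | 96 |
| Quade minus after | −2 | 0 | +6 | +15 | +19 |
| Quade minus change | +18 | +14 | +6 | −2 | −3 |

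At rho 0, power is 77% on after values, 48% on change and 74% with Quade. For a 1.0 SD effect at rho 0.2/0.3/0.5/0.7/0.8, it is 44% throughout on after values, 30/33/44/64/81% on change and 43/45/51/63/74% with Quade. Type I error of Mann-Whitney and Quade is 4.7% to 5.4% in all settings.

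**5. Sensitivity.**

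- If SD(after)/SD(before) is 0.7, change has 41/57/76/88% at rho 0.2/0.5/0.7/0.8, against 75/83/92/96% for Quade. If the ratio is 1.43, change has 69/86/97/99% and Quade is unchanged.
- Rounding readings to whole units leaves Quade at 4.9% to 5.2% type I error.

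**6. Why a rank method.** Raw-scale ANCOVA is better on normal data (78/80/87/96/99% at the five values of rho). On lognormal data (log SD 0.8) with a multiplicative effect it falls to 59/61/67/80/88%, against 77% for Mann-Whitney on after values and 75/77/83/92/96% for Quade. With an additive shift at rho 0.2/0.3/0.5 it has 83/84/88%, against 90% for Mann-Whitney on after values.

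**7. Chance imbalance.** The SE of the baseline difference is √(2/8) = 0.50 SD. A gap of 1.0 SD or more is 2 SE and has a 4.6% chance. Under no effect, a gap G shifts the after-value comparison by rho × G and the change comparison by −(1 − rho) × G. With G = 1.0 SD, false-positive rates over the five values of rho are 6/7/12/18/23% on after values, 16/15/12/9/8% on change and 3% to 4% with Quade. With G = 0.5 SD all stay at about 5% or below.

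**8. Unnamed variable.** If whichever version is more favourable could be reported, the false-positive chance is about 9%. At 1.5 SD the two versions disagree in 23% to 32% of trials.

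**9. Unit.** If 32 canines were treated as independent, type I error would be 8/10/13% at an assumed intraclass correlation of 0.3/0.5/0.7. With patient means it is 5.0% to 5.2%.

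**The case against.** The strongest reply is that nothing here is invalid. An unadjusted Mann-Whitney test on one value per patient is a legitimate analysis of a randomised trial, and over all randomisations its error is 5%. That stands: the point concerns efficiency and specification.

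Second, if change was intended, the baseline is already used, and at high correlation Quade is worse. That also stands. At rho 0.8 the loss is 3 points for a 1.5 SD effect and 7 points for 1.0 SD. But rho is unknown, and each reading of the plan has a weak region. With normal data, equal SDs and a 1.5 SD effect, Quade is never more than about 3 points below the better version over rho 0 to 0.8.

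Third, 1.5 SD is a large effect. At 0.5 SD after values have 15% power and Quade 15% to 27%, with a gain of only 0 to 2 points up to rho 0.5. A covariate does not repair a sample that was never sized for EPT.

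Fourth, the high conditional error rates need a rare imbalance, and the canine-level figures concern a separate matter, since the documents do not say that canines were analysed as independent. Both are fair limits on the weight those figures carry.

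Fifth, putting Quade and raw ANCOVA beside the planned test yields three p values. The chance that at least one is significant under no effect is 7% to 10%. Naming one main analysis and labelling the rest limits this, but cannot make a late analysis prespecified.

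**Conclusion.** The concern holds, as an improvement the sponsor should make rather than an error that invalidates the result. The documents show a baseline that is collected, a between-group test that takes no covariate, and no statement of the variable or the unit. The size depends on quantities they do not give: rho, the EPT distribution and an effect of interest. Across the assumed range the benefit runs from a small loss at low correlation, relative to after values, to 19 points of power at rho 0.8. Relative to change it runs from an 18-point gain at rho 0.2 to a loss of 3 points at rho 0.8 (7 for a 1.0 SD effect). Confidence in the size is therefore medium. The need to name the variable and the unit does not depend on these assumptions. Nothing in the documents shows that a version was chosen for its result.

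**What to change.** 1. Reduce EPT to one value per patient at each time, the mean of the two canines.
2. As the single main EPT analysis, compare groups on after-retraction EPT by Quade's rank ANCOVA with before-retraction EPT as covariate. This matches the plan's own description of its data as non-parametric.
3. Report raw-scale ANCOVA, with adjusted difference and 95% CI, as a secondary analysis. Quade gives a p value but no difference in EPT units. Allow no data-dependent switch between the two.
4. State whether the planned Mann-Whitney test used after values or change, and on which unit.

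No new data are needed; the statistical price is one degree of freedom and the small power losses shown above. Because the study ended in October 2022, the adjusted analysis must be labelled as added after the fact, unless it was prespecified, and reported beside the planned Mann-Whitney result.
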